# 9.11 The type and duration of the follow-up of subjects after adverse events.

Follow up for any AE, SAE, AR or SAR will be until the event has resolved or 30 days after baseline. This follow up will be via telephone consultation and the written and electronic record. Any SUSAR related to the IMP will need to be reported to the Sponsor irrespective of how long after IMP administration the reaction has occurred.

# 9.12 Development safety update reports (DSUR)

The PI will provide (in addition to the expedited reporting above) DSURs once a year throughout the clinical trial, or on request, to the MHRA in the UK, Ethics Committee, Host NHS Trust and Sponsor.

The report will be submitted within 60 days of the MHRA clinical trial authorisation of the trial each year until the trial is declared ended.

# 10 STATISTICS AND DATA ANALYSIS

All statistical analysis will be carried out using SPSS or R software provided by the University of Hull.

# 10.1 Sample size calculation

The study is designed as a pilot and exploratory study but we have performed a power calculation in order to ensure the results form a reliable basis to inform future work and to gauge an appropriate timeline for recruitment (and thus will influence any future funding). The calculation may appear crude as we are limited by the lack of reliable data on net fluid loss and serum chloride concentrations in patients receiving high dose diuretics (table 1 and table 2).

# Net fluid loss

Current guidelines recommend a target of ~1000ml net fluid loss per day during in-patient diuresis, which generally occurs over a period of up to 9 days (median length of stay for a patient hospitalised with heart failure in the UK). We estimate that a clinically significant difference in daily net fluid loss is 500-1000 ml – a minimum of 4.5L over a 9 day period and 2L over the 4 day period of our study. Such an increase in net fluid loss would indicate a significant increase in diuresis that may shorten hospital admission.

Using the available data on urine output (appendix 7), we expect an average daily fluid loss of 1000ml per day with a standard deviation ranging from 500-1000ml. Patients admitted with heart failure are often breathless on very modest exertion thus we anticipate a drop-out rate of 10% in the control arm. Furthermore, given the lack of reliable clinical data on the tolerability of acetazolamide we have anticipated a higher drop-out rate of 20% in the acetazolamide arm. Thus, to detect a difference of

500-1000ml in net fluid loss per day with statistical power of 80% and two-tailed significance of 5% we would need to recruit a minimum of 35 patients (17 in the control arm and 18 in the acetazolamide arm).

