# 3.4 **Primary endpoint/outcome**

Difference in mean net fluid loss daily and over a 4 day period

• Total volume intake in millilitres (mL) – total volume passed as urine in mL

Difference in serum chloride concentrations between day 1 and day 4

• Serum chloride day 4 – serum chloride day 1

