# 10.3 Statistical analysis plan

# Baseline data

# Primary outcomes

Differences in daily net fluid loss and total change in serum chloride (day 1 to day 4) will be compared using independent samples T test. If a difference in number of hours of furosemide per day or salt intake per day is different between the groups then the change in the primary outcomes will be stratified sub groups of hours of furosemide per day and grams of salt per day (cut-offs for group membership will be identified post-hoc).

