# Appendix 2 – Data to support power calculations

#### Net Fluid Loss

Of the recently published trials of diuretics in patients admitted with heart failure (table 1) the DOSE trials provides the most reliable data on which we can base a power calculation: a similar patient population was recruited, patients taking diuretics other than loop diuretics were ineligible and patients in the high-dose arm received an average of 260mg IV furosemide per day. Net fluid loss over a 3-day period was 4899 ±3479 mL in the high-dose arm equating to 1633 ±1160 mL per day.

The other comparable data come from the control arm of the ATHENA study (table 1) in which patients received an average of 120mg IV furosemide per day. Median net fluid loss over a 4-day period was 5584 (2924-8132).

Table 1 - Net fluid loss in recent trials involving high dose intravenous loop diuretic

Trial	N (trial arm)	Diuretic dose per day (mean)	Time period over which UO was measured	Net fluid loss (ml)
DOSE	151 (low dose)	120mg	72 hours	3575 ±2635
	157 (high dose)	260mg	72 hours	4899 ±3479
TACTICS- HF		140mg	24 hours – Day 1	1541 ±1525
	128 (placebo)		24 hours – Day 2	1419 ±1379
			24 hours – Day 3	1401 ±1387
ATHENA- HF†	178 (standard care)	120mg	24 hours	1183 (510-1955)
			48 hours	2282 (1155-4135)
			72 hours	3810 (2011-5565)
			96 hours	5584 (2924-8132)
UNLOAD	100 (standard care)	180mg	48 hours	3300 ±2610
CARESS- HF	94 (standard care)	NR	96 hours	7082 ±4183

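### The daily SD of 500-1000 mL behind the fluid-loss sample size lies below every single-day spread in the protocol's own Appendix 2, so the stated 80% power is not supported, least of all for 500 mL per day.

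*Protocol*

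**What the plan says.** Section 3.4 defines the fluid co-primary as "Difference in mean net fluid loss daily and over a 4 day period". Section 10.3 then states: "Differences in daily net fluid loss and total change in serum chloride (day 1 to day 4) will be compared using independent samples T test". Section 10.3.2 likewise compares each day's loss as well as the loss from baseline to day 4.

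The planning assumption in section 10.1 is "we expect an average daily fluid loss of 1000ml per day with a standard deviation ranging from 500-1000ml". It is said to rest on available data in an appendix; the text points to appendix 7, but the data are in Appendix 2. The target is "500-1000ml in net fluid loss per day with statistical power of 80% and two-tailed significance of 5" per cent. Loss is allowed for in each arm: "we anticipate a drop-out rate of 10% in the control arm", and a "higher drop-out rate of 20% in the acetazolamide arm". The conclusion is a "need to recruit a minimum of 35 patients (17 in the control arm and 18 in the acetazolamide arm"). The trial summary plans 40 patients with a maximum of 50, and section 7.3.1 allocates them 1:1.

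Appendix 2 names the DOSE trial as the best available basis for the calculation and reports: "Net fluid loss over a 3-day period was 4899 ±3479 mL in the high-dose arm equating to 1633 ±1160 mL per day". Table 1 there lists net fluid loss from five trials over periods of 24 to 96 hours.

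**The concern.** If each day's loss is compared between arms, the SD that governs power is the SD of one day's loss. No single-day figure in Table 1 is as low as 1000 mL, the top of the assumed range. The preferred source also exceeds it, even though its figure averages over three days. The bottom of the range, 500 mL, is well below anything in the table.

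The protocol is a pilot, but section 4 describes it as powered for superiority on both primary endpoints. Section 10.1 says the calculation is there so that the results form a sound basis for later work, and section 2 makes a larger trial depend on a favourable signal. If power is lower than stated, a non-significant daily comparison carries less information than readers will be led to think.

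**Working it through.** **Step 1: the plan's own figure.** Difference and SD are both given as ranges and are not paired. Only pairs with difference/SD = 1 (500/500 or 1000/1000) come near 35. At that ratio, 80% power at two-sided 5% needs 16 per arm (normal approximation) or 17 (t-test). Dividing by 0.9 and 0.8 for drop-out and rounding up gives 18 + 20 = 38 or 19 + 22 = 41, so 35 does not follow exactly. With 35 recruited:

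- Evaluable: 17 × 0.9 = 15.3 and 18 × 0.8 = 14.4.
- Power at ratio 1 (t-test): 75% after drop-out; 82% if nobody drops out.
- Power for 500 mL with SD 1000 mL, both inside the stated ranges: 26%.

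The claim for 500 mL therefore depends wholly on an SD of 500 mL.

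**Step 2: what Appendix 2, Table 1 supports.** Interquartile ranges are converted as width/1.349, which assumes normality. For the ATHENA-HF 24-hour row the quartiles lie 1183 − 510 = 673 below and 1955 − 1183 = 772 above the median, so this is a fair approximation.

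| Source | Period | SD per day (mL) | Kind |
|---|---|---|---|
| TACTICS-HF placebo | days 1, 2, 3 | 1525, 1379, 1387 | single day |
| ATHENA-HF | 24 h | (1955 − 510)/1.349 = 1071 | single day |
| DOSE high dose | 72 h | 3479/3 = 1160 | 3-day average |
| DOSE low dose | 72 h | 2635/3 = 878 | 3-day average |
| UNLOAD | 48 h | 2610/2 = 1305 | 2-day average |
| CARESS-HF | 96 h | 4183/4 = 1046 | 4-day average |
| ATHENA-HF | 48 h | (4135 − 1155)/1.349/2 = 1105 | 2-day average |
| ATHENA-HF | 72 h | (5565 − 2011)/1.349/3 = 878 | 3-day average |
| ATHENA-HF | 96 h | (8132 − 2924)/1.349/4 = 965 | 4-day average |

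All single-day values exceed 1000 mL. The smallest value of any kind is 878 mL.

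**Step 3: power for a single day.** Two-sided 5% t-test with noncentrality δ/(SD × √(1/n₁ + 1/n₂)). Evaluable numbers are 15.3/14.4 at 35; 20 × 0.9 = 18 and 20 × 0.8 = 16 at 40; and, with the 23/27 split in section 10.1, 20.7/21.6 at 50. Example: 1000 mL, SD 1071, 35 recruited: √(1/15.3 + 1/14.4) = 0.367, noncentrality 1000/(1071 × 0.367) = 2.54, power 69%.

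| SD (mL) | 35: 1000 / 500 mL | 40: 1000 / 500 mL | 50: 1000 / 500 mL |
|---|---|---|---|
| 1000 (plan's maximum) | 75% / 26% | 81% / 29% | 89% / 36% |
| 1071 | 69% / 23% | 75% / 26% | 84% / 32% |
| 1160 | 62% / 21% | 68% / 23% | 78% / 28% |
| 1379 | 48% / 16% | 54% / 18% | 63% / 21% |
| 1525 | 41% / 14% | 46% / 15% | 55% / 18% |

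**Step 4: the 4-day total.** The SDs are 3861 mL (ATHENA-HF 96 h, 5208/1.349), 4183 mL (CARESS-HF) and 4639 mL (DOSE high dose, 3479 × 4/3, which assumes the daily average varies as much over four days as over three). At 35 recruited, power for 4 L is 78%, 71% and 62%. For 2 L, which section 10.1 gives as the minimum clinically significant difference over four days, it is 28%, 24% and 21%.

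**Step 5: detectable difference.** Solving the same formula for 80% power gives about 0.993 × SD at 40 recruited and 0.883 × SD at 50. For a single day with SD 1071-1525 mL that is about 1.06-1.51 L at 40 and 0.95-1.35 L at 50. For the 4-day total with SD 3861-4639 mL it is about 3.8-4.6 L and 3.4-4.1 L.

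**The case against.** A reader might infer that power is simply halved. The documents do not support that as a general statement. It holds only with the TACTICS-HF SDs, a 1000 mL difference and 35-40 recruits. Those SDs come from one arm of one trial; the other single-day row, ATHENA-HF, implies 1071 mL. At that SD power for 1000 mL is 69% at 35, only 6 points below the 75% obtained with SD 1000, and it reaches 84% at 50.

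A reader might also infer that the assumed range came from mistaking the SD of a multi-day average for the SD of one day. The protocol never says how 500-1000 mL was derived, so this is conjecture. The 1160 mL figure is correct arithmetic for a 3-day average and lies outside the range anyway. Within ATHENA-HF, going from 24 to 96 hours lowers the per-day SD only from 1071 to 965 mL.

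Section 10.1 speaks of average daily loss and converts 500 mL per day into 2 L over four days, so the SD of a multi-day average is a natural reading. On that scale 878 and 965 mL fall inside the range, and the upper end, 4 × 1000 = 4000 mL over four days, is close to the ATHENA-HF figure of 3861 mL. For a 4 L difference the plan is then not far off.

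Finally, the protocol calls the calculation crude, and section 4 names feasibility and tolerability as the primary aim. This limits the consequence. It does not explain an SD range that excludes both the protocol's preferred source and its single-day rows.

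**Conclusion.** The concern stands in this form. The planning SD is too low for the daily comparison, its lower end of 500 mL is unsupported on any scale, and the 80% claim for 500 mL per day cannot be sustained. Across the single-day SDs in Appendix 2 (1071-1525 mL), power for 1000 mL per day is 69-41% at 35 recruited, 75-46% at 40 and 84-55% at 50. For 500 mL per day it is 23-14%, 26-15% and 32-18%. For the 4-day total, power at 35 is 78-62% for 4 L and 28-21% for 2 L.

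These figures assume the stated drop-out, a t-test with equal variances, normality when converting interquartile ranges, and that variability in this trial resembles that in the cited ones. The width of the ranges reflects real disagreement between the sources. How the range of 500-1000 mL arose is unknown, and the conclusion does not depend on it.

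**What to change.** In section 10.1:

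- Replace the SD range with one SD for each scale analysed: a value within about 1070-1525 mL for a single day and within about 3900-4600 mL for the 4-day total. Cite the Table 1 row used for each, and correct the appendix number.
- Remove the SD of 500 mL.
- Restate power or detectable difference at 40 and 50 patients, pairing each difference with its SD, and withdraw the 80% claim for 500 mL per day.

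In Appendix 2, keep the 1160 mL figure but label it as the SD of a 3-day average.

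This is a change of wording only. It needs no extra patients and leaves the primary endpoint and its tests as they are. Making the 4-day total the only powered fluid endpoint would be a separate design choice and is not required here. The one cost is a less favourable statement of power.

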# 4 TRIAL DESIGN

This will be an open label, randomised, controlled pilot and exploratory study which will be powered to detect superiority of the addition of acetazolamide 250mg BD by mouth (PO) in conjunction with 240mg/24 hours furosemide IVI on diuresis and chloride homeostasis compared to 240mg/24 hours IV furosemide infusion alone (standard of care) both primary endpoints with the primary aim of gathering data on the feasibility and tolerability of the intervention which will inform a larger study.

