# Serum chloride concentrations

Low serum chloride is associated with adverse outcome in patients with HF. We estimate a clinically meaningful change in chloride to be -0.9 mmol/L per day over the course of an admission (9 days) and -3.6 mmol/L over the four day period of our study (appendix 7). To detect such a difference with 80% power and 5% two-tailed significant with the above anticipated drop out rate we would need to recruit a minimum of 14 patients in the control arm and 17 patients in the ACZ arm.

We expect two potential confounding factors for the co-primary endpoints: 1) daily salt intake and 2) loss of IV access reducing the amount of IV furosemide given. We will collect data on both potential confounders using a daily dietary sheet (on which the patient will record their meals for the day and from which the daily salt intake will be estimated) and recording the "number of hours of furosemide" per day. We do not expect any patient to have excessive salt intake (defined by the European Society of Cardiology Heart Failure Guidelines 2021 as >5g per day). Any patient with >5g salt intake per day or <20 hours of furosemide per day will be removed from the analysis. Due to the exploratory nature of the study we will conduct an intention to treat analysis and a per-protocol analysis in which only patients who completed the study without deviating from the protocol will be included. Thus, we will recruit a maximum of 50 patients – 23 in the control arm and 27 in the ACZ arm with anticipated drop out of 10% and 20% respectively. The extra patients recruited will also act as a contingency should any patient need to be removed from the analyses for reasons of excess salt intake, prolonged loss of IV access, or for the per-protocol analysis.

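### The minimum of 35 patients for net fluid loss does not give 80% power from its own inputs, and 80% power is not met across the stated 500-1000 mL/day range

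*Protocol*

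**What the plan says.** Section 4 of the Protocol describes a pilot and exploratory study "which will be powered to detect superiority" on both primary endpoints. In section 10.1 (Net fluid loss) the sponsor judges that "a clinically significant difference in daily net fluid loss is 500-1000 ml", which it converts to "a minimum of 4.5L over a 9 day period and 2L over the 4 day period of our study". It expects a loss of 1000 mL per day "with a standard deviation ranging from 500-1000ml", with drop-out of 10% in the control arm and 20% in the acetazolamide arm. From these it concludes that, to detect a difference of "500-1000ml in net fluid loss per day with statistical power of 80% and two-tailed significance of 5"%, it must "recruit a minimum of 35 patients (17 in the control arm and 18 in the acetazolamide arm").

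The chloride part of section 10.1 sets the maximum of 50 as "23 in the control arm and 27 in the ACZ arm". The Trial Summary gives a planned sample of 40 with a maximum of 50, and section 7.3.1 specifies 1:1 allocation in a permuted block of up to 50. Appendix 2 treats the high-dose arm of the DOSE trial as the most reliable basis for the calculation, with net fluid loss "equating to 1633 ±1160 mL per day".

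**The concern.** Two ranges and one power target cannot lead to a single sample size unless one difference and one SD are chosen, and section 10.1 names neither. The figure of 35 follows directly from the drop-out rates, so it is presented as already allowing for them, yet 17 and 18 are close to what a t-test needs before any drop-out. The assumed SD range also stops short of the SD in the source that Appendix 2 prefers.

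Section 10.1 says the calculation is there so that the results form a reliable basis for future work. A reader who takes it at face value would believe that the trial has an 80% chance of detecting 500 mL/day (2 L over 4 days). Whether it does depends almost entirely on an SD that the protocol leaves open by a factor of two.

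**Working it through.** **Inputs.** Difference 500-1000 mL/day; SD 500-1000 mL; power 80%; two-sided 5%; drop-out 10% (control) and 20% (acetazolamide), all from section 10.1. Independent-samples t-test, from section 10.3. Alternative SD of 1160 mL/day, from Appendix 2 (3479/3).

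**Step 1: try to reproduce 35.** The number per arm is n = 2(1.96 + 0.84)²/(difference/SD)². The stated figure is approached only when the difference equals the SD (500/500, 750/750 or 1000/1000):

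- Normal approximation: n = 15.7, so 16 evaluable per arm. Recruited: 16/0.9 = 17.8 and 16/0.8 = 20, so 18 + 20 = 38.
- t-test (noncentral t): 16 per arm gives 78.1% and 17 gives 80.7%, so 17 evaluable per arm. Recruited: 17/0.9 = 18.9 and 17/0.8 = 21.3, so 19 + 22 = 41.

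Neither is 35. Two routes come close: ignoring drop-out (17 and 18 evaluable give 81.9%), or multiplying instead of dividing and rounding down (15.7 × 1.1 = 17.3; 15.7 × 1.2 = 18.8). The protocol does not say what was done, so the origin is conjecture.

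**Step 2: power after drop-out, without replacement.** Evaluable numbers are:

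- 35 recruited: 17 × 0.9 = 15.3 and 18 × 0.8 = 14.4
- 40 recruited (20/20): 18 and 16
- 50 recruited (25/25): 22.5 and 20

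| Difference / SD (mL/day) | 35 | 40 | 50 |
|---|---|---|---|
| 500/500 or 1000/1000 | 75% | 81% | 89% |
| 500/750 | 42% | 47% | 56% |
| 500/1000 | 26% | 29% | 36% |
| 500/1160 | 21% | 23% | 28% |
| 1000/1160 | 62% | 68% | 78% |
| 1000/500 | >99% | >99% | >99% |

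For 80% power, 500 mL/day with SD 1000 needs 64 evaluable per arm: 64/0.9 = 71.1 and 64/0.8 = 80, so 72 + 80 = 152 recruited. A split of 23/27 (20.7 and 21.6 evaluable) gives the same power as 25/25 to within 0.1 percentage point in the 500 mL and equal-to-SD rows.

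**Step 3: which SD does Appendix 2 support?** Dividing the SD of a cumulative total in Table 1 by its number of days gives:

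- DOSE low dose: 2635/3 = 878
- DOSE high dose: 3479/3 = 1160
- UNLOAD: 2610/2 = 1305
- CARESS-HF: 4183/4 = 1046
- ATHENA-HF, 96 hours: (8132 - 2924)/1.349 = 3861, and 3861/4 = 965 (assumes normality)

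The single-day SDs in TACTICS-HF are 1379-1525. None is near 500.

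**Step 4: what can be detected with 80% power?** The standardised difference is 0.993 with 40 recruited and 0.882 with 50. For SD 1000-1160 this is about 990-1150 mL/day with 40 and about 880-1020 mL/day with 50.

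**Step 5: 4-day total.** For 2 L with the SDs from the 96-hour sources (3861 and 4183 mL), power is 28% and 24% with 35 recruited, 31% and 27% with 40, and 38% and 33% with 50.

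**The case against.** The best defence is that 35 is a floor, not the plan. The Trial Summary plans 40, and 40 gives about 81% when the difference equals the SD, so the drop-out slip has no consequence at the planned size in that case. This stands.

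The protocol also intends to replace patients who withdraw before completing day 4 (section 7.9) or lack primary-endpoint data (section 10.7). If every loss were replaced, 17 and 18 evaluable would give about 82%. Replacement is only attempted, however, and section 10.1 presents 35 as covering drop-out without it. Full replacement would also leave 500 mL/day with SD 1000 at only 30%.

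The study calls itself a pilot, admits that the calculation may look crude, names feasibility and tolerability as its primary aim (section 4) and says it is not designed to detect a treatment benefit (section 13.10). That lowers the stakes. It does not make the stated power correct, and it sits awkwardly with the superiority claim in section 4. No passage says that a null result would be taken to exclude 500 mL/day; that misuse is a risk, not a plan.

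Some stronger readings are tempting but unsupported. A reader might take 75% as the best case, but the stated ranges also allow 1000 mL with SD 500, where power exceeds 99%. A reader might take 21-26% as the power of 35 patients at 500 mL/day whatever the SD; it requires SD 1000-1160, and at SD 500 power is 75%. Nor is a 23/27 split impossible: section 7.3 speaks of simple randomisation, under which it can occur by chance. It conflicts with section 7.3.1 only as a planned target.

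**Conclusion.** The point holds in two parts. First, 35 recruited does not give 80% power from the stated inputs: in the nearest case (difference equal to SD) 41 are needed with a t-test, or 38 by the normal approximation, and 35 gives about 75%. Recruiting the planned 40 closes this gap.

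Second, 80% power is claimed for the whole 500-1000 mL range with SD 500-1000 mL, and neither 40 nor 50 patients achieve it. At the minimum difference with SD 1000, power is about 29% and 36%; with the Appendix 2 figure of 1160 it is about 23% and 28%. The claim at 500 mL/day could be true only with an SD at or near 500, which no source in Table 1 supports.

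These figures assume a two-sided t-test, equal SDs in the two arms, drop-out as stated and no replacement. They do not count removals for salt intake above 5 g or under 20 hours of furosemide per day, which would lower power further unless those patients are replaced. The 1160 figure is a 3-day total divided by three, so it is strictly the SD of a daily mean over three days, not of a single day.

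**What to change.** Keep 40-50 patients and restate section 10.1:

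- Name one difference and one SD, taken from Appendix 2 on the same time scale as the endpoint: about 1000-1160 mL/day for daily loss, or about 3900-4200 mL for the 4-day total from the 96-hour sources (the lower figure assumes normality). Do not pair the DOSE daily figure with the 96-hour totals: 4 × 1160 = 4640 mL, which is not the same quantity.
- Inflate by 1/(1 - drop-out).
- Replace 17/18 and 23/27 with equal arms consistent with 1:1 randomisation.
- State the difference detectable with 80% power: about 990-1150 mL/day with 40 recruited and about 880-1020 mL/day with 50, for SD 1000-1160.
- Remove the claim of 80% power at 500 mL/day, and bring the superiority wording in section 4 into line.

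The cost is protocol wording and a less favourable power statement. No extra patients are needed.
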